4.4.4 Follow-Up Visits

The following longitudinal data will be collected for all follow-up clinic visits through final follow-up:

- Work status / ADL
- Compliance with postoperative protocol/restrictions (if applicable)
- VAS (as available)
- ODI (as available)
- Patient satisfaction (as available)
- Complications
- Secondary treatments
- Narcotics use
- Diagnostic Imaging
- Incidence of Epidural Steroid Injections (ESI)

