2.2 Secondary Objectives

The secondary objectives of this study are:

- To measure and compare patient reported outcomes (e.g., VAS, Patient Satisfaction and ODI) at baseline and final follow-up
- To measure and compare clinical and radiologic outcomes at baseline and final follow-up
- To measure and compare the clinical, radiologic, and patient reported outcomes at interim follow-up visits
- To assess the impact of demographics and risk factors on clinical, radiologic, and patient reported outcomes

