3.2 Exclusion criteria

There are no exclusion criteria for this study.

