4.4.2 Surgical Treatment Visit

- Operative Summary
 - Date of surgery
 - Surgical procedure
 - Operative time
 - Estimated blood loss
 - Anesthesia details
 - Treated level(s)
 - Device size
 - Intra-operative/early post-operative complications, such as:
 - Dural tears
 - Hematomas
 - Fractures
 - Nerve injury
 - Diagnostic imaging History
 - Dictated operative notes
- Repeat Surgery Summary
 - Date of surgery
 - Reason for surgery (reoperation, revision, removal, etc.)
 - Surgical procedure
 - Operative time
 - Estimated blood loss
 - Anesthesia details
 - Treated level(s)
 - Surgical intervention performed
 - Device size
 - Intra-operative/early post-operative complications

- Dural tears
- Hematomas
- Fractures
- Nerve injury
- Diagnostic imaging History

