5.0 Statistical Analysis

5.1 General Information

All continuous outcome measurements at follow-up time points will be compared to baseline values using a t-test for superiority. Categorical outcome measurements will be compared using a Fisher's exact test for superiority. Statistical significance for these analyses will be demonstrated with a p-value less than 0.05.

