5.2 Primary Endpoint

Overall duration of follow-up care and incidence of secondary surgical interventions will be analyzed to evaluate overall effectiveness of the use of the coflex® Interlaminar Technology

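### The plan has no rule for scores recorded after a repeat operation, so the comparison with baseline attributes them to the index procedure

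*Combined protocol and SAP*

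**What the plan says.** **Collection.** Section 4.4.4: "The following longitudinal data will be collected for all follow-up clinic visits through final follow-up". The list that follows includes VAS, ODI, satisfaction, narcotics use and imaging. Nothing ends collection at a repeat operation.

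**Analysis.** Section 5.1: "All continuous outcome measurements at follow-up time points will be compared to baseline values using a t-test for superiority". The significance rule is "Statistical significance for these analyses will be demonstrated with a p-value less than 0.05". Section 2.2 makes the last visit the reference point: "To measure and compare patient reported outcomes (e.g., VAS, Patient Satisfaction and ODI) at baseline and final follow-up" and "To measure and compare clinical and radiologic outcomes at baseline and final follow-up". Final follow-up is not defined in relation to a repeat operation.

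**Repeat surgery.** Section 4.4.2 has a block for repeat operations with the date, procedure, treated levels and "Reason for surgery (reoperation, revision, removal, etc" among its items. Section 5.2 uses the event itself: "Overall duration of follow-up care and incidence of secondary surgical interventions will be analyzed to evaluate overall effectiveness".

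**Exclusions.** Section 3.2: "There are no exclusion criteria for this study". Reoperated patients therefore stay in the study population.

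No section censors values after a repeat operation, scores them as failure or reports them separately, and no sensitivity analysis is planned.

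**The concern.** After a device has been removed or a level revised, a later ODI score or radiograph reflects the second operation at least as much as the first. The title announces an evaluation of the performance of coflex against decompression with or without fusion. Under the plan, one patient can count as a secondary surgical intervention under section 5.2 and also contribute a good final ODI to the result of the index procedure.

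Sections 1.0 and Risk/Benefit Assessment say that the data will support publications and marketing. A reader of a published mean change would need to know whether it describes the index procedure alone or the index procedure plus whatever surgery followed. Fixing the time of final follow-up would not settle this, because a visit at a common time can still fall after a repeat operation.

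**Working it through.** The plan gives no sample-size calculation, reoperation rate, effect size or standard deviation, so there is no figure of its own to reproduce. The check has two parts.

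**1. Does the text send these values into the comparison?**
- Section 4.4.4 collects every clinic visit up to the last.
- Section 5.1 compares all continuous follow-up values with baseline.
- Section 2.2 compares baseline with final follow-up.
- Section 3.2 removes nobody.
- Section 4.4.2 records the date that could separate earlier from later values, but section 5 never uses it for that purpose.

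Retention is thus the natural reading. It is inferred from the word *all* and the lack of any exception; no sentence states it outright.

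**2. How large could the effect be?** Define:
- r = share of analysed patients reoperated before final follow-up (assumed)
- m = mean improvement in patients without reoperation (assumed)
- b, a = mean improvement in reoperated patients at the last score before reoperation and at final follow-up (assumed)
- d = a − b

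Mean change with all visits = (1 − r)m + ra. 
Mean change with values before reoperation = (1 − r)m + rb. 
Difference = r(a − b) = rd. The value of m drops out.

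Example with r = 10%, m = 25, b = 0, a = 20 ODI points:
- all visits: 0.9 × 25 + 0.1 × 20 = 24.5
- before reoperation: 0.9 × 25 + 0.1 × 0 = 22.5
- difference: 0.1 × 20 = 2.0

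Shift in mean change (points on a 0–100 score, all inputs assumed):

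| r | d = −10 | d = 0 | d = 10 | d = 20 | d = 30 |
|---|---|---|---|---|---|
| 5% | −0.5 | 0 | 0.5 | 1.0 | 1.5 |
| 10% | −1.0 | 0 | 1.0 | 2.0 | 3.0 |
| 20% | −2.0 | 0 | 2.0 | 4.0 | 6.0 |

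**Against sampling error.** With an assumed SD of change of 20, the 95% half-width is 1.96 × 20/√n. This is 1.75 points at n = 500 and 0.55 at n = 5000. The Protocol Summary plans about 5000 patients, but section 5.3 collects scores only as available, so the number with paired scores is unknown. A 2.0-point shift exceeds both half-widths. A 1.0-point shift exceeds only the second, and a 0.5-point shift exceeds neither. A larger sample narrows the interval but leaves the shift unchanged.

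**The case against.** **Keeping all scores is a legitimate choice.** A treatment-policy comparison describes how treated patients fare, whatever happens next. The Purpose line in the Protocol Summary, which speaks of the outcomes of treated patients, is compatible with that. This stands as a reason not to discard the all-visits analysis. It does not excuse leaving the choice unstated and without a second analysis beside it.

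**Section 4.4.4 governs collection, not analysis.** True, and any handling of reoperation needs complete collection. The gap arises because sections 5.1 and 2.2 then use the values without exception.

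**Reoperations are not hidden.** A reader might infer that failures disappear from the study. They do not: section 5.2 puts their incidence in the primary endpoint. The problem is confined to the score, clinical and radiologic comparisons. Sections 2.2 and 5.3 treat these as secondary, although section 4.1 places patient-reported outcomes under the primary objective.

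**Direction.** A reader might infer that improvement is necessarily overstated. That holds only if repeat surgery improves scores, and the documents give no evidence either way.

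**Comparison between treatments.** A reader might also infer that a difference between coflex and decompression is masked. Section 5 specifies no between-group test of VAS or ODI, so there is no planned contrast to measure this on. The fraction of a gap that would vanish is (a − b)/(m − b) when the groups differ only in reoperation rate. It is set by the assumed improvements and would be no finding about this study.

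**The last score before reoperation is not neutral.** It may be early and taken when the patient is at their worst, so it could bias the mean the other way. Because scores are as available, some patients will have none. This is why it belongs in a sensitivity analysis and should not replace the main one.

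**Conclusion.** The concern holds in this form: followed as written, the plan attributes values recorded after a removal, revision or other reoperation to the index procedure, and the incidence analysis in section 5.2 does not correct the affected comparisons. The shift is the reoperation share times the score change after reoperation. It is 1 to 4 ODI points at assumed shares of 5% to 20% with an assumed 20-point gain, and 0.5 to 6.0 points over gains of 10 to 30. It is zero or negative if repeat surgery does not help. All these inputs are assumptions. What the documents themselves support is the missing rule; the size and sign remain unknown until the data are seen. The rule should be stated before analysis.

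**What to change.** Keep the all-visits comparison and label it as including values after reoperation. In sections 5.1 and 5.3 add:

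- **(a) Proportion improved.** Use a prespecified threshold for improvement, and count any patient with secondary surgery at a treated level as not improved. This also covers reoperated patients with no score before the second operation. State the denominator and report how many patients entered it through a score and how many through secondary surgery, because non-reoperated patients without scores cannot be classified.
- **(b) Sensitivity analysis.** Repeat the comparison with baseline using only values before the repeat-surgery date collected under section 4.4.2, and report how many reoperated patients have no such value.

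A further analysis ending at the first epidural steroid injection is optional. Section 4.4.4 lists the incidence of injections but no injection date, so visit dates might have to stand in.

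**Cost.** Some SAP wording, one threshold to choose in advance, and a date comparison. The repeat-surgery date is already collected. Section 4.4.4 does not list a follow-up visit date, but the follow-up duration endpoint in section 5.2 implies that one is recorded. The downside is a little more analysis and a possibly less favourable improvement figure.

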4.2 Data Collection Summary

Subjects will have undergone a decompression surgery with the coflex® Interlaminar Technology, 1 or 2 level decompression with or without fusion according to the physician's standard procedures. Table 1 describes the anticipated time points which will be collected as part of the retrospective data review. Please see Section 4.4, Data Collection Procedures for additional details regarding the data points intended to be captured at the designated time points.

	Baseline	Surgical Treatment	Post-Operative Hospital Stay	Follow-Up Visit(s)
Demographics & Risk Factors	X			
Prior Surgery Detail (If available)	X			
Diagnosis	X			
Operative Summary		X		
Procedure Payer Information		X		
Secondary Treatments			X	X
Complications		X	X	X
Work Status / ADL (If available)	X		X	X
Patient Questionnaires (If available)	X	X	X	X
Diagnostic Imaging History	X	X	X	X

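### Interim comparisons with baseline have no defined time points and no rule for several visits from one patient, so the planned tests rest on an unstated grouping of visits

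*Combined protocol and SAP*

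**What the plan says.** Three parts of the combined protocol and SAP bear on this.

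- **Collection.** Section 4.4.4 states: "The following longitudinal data will be collected for all follow-up clinic visits through final follow-up". VAS, ODI and satisfaction are taken only where the chart has them. Section 4.2 says "Table 1 describes the anticipated time points which will be collected as part of the retrospective data review", but the table has one undivided follow-up column, with no visit names, target days or windows.
- **Objectives.** Section 2.2 lists "To measure and compare the clinical, radiologic, and patient reported outcomes at interim follow-up visits". It also lists a separate comparison with the last visit: "To measure and compare patient reported outcomes (e.g., VAS, Patient Satisfaction and ODI) at baseline and final follow-up".
- **Analysis.** Section 5.1 states: "All continuous outcome measurements at follow-up time points will be compared to baseline values using a t-test for superiority". For categorical outcomes: "Categorical outcome measurements will be compared using a Fisher's exact test for superiority". The threshold is "Statistical significance for these analyses will be demonstrated with a p-value less than 0.05".

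No section says whether the t-test is paired, which visits make up a time point, how many values a patient may contribute to one, or that repeated measurements will be modelled as such.

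**The concern.** Both named tests assume independent observations. The data will hold an unfixed number of visits per patient, at times set by routine care. Using the plan without adding to it, an analyst has two options, and each has a fault.

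- **Pool the visits.** A patient, and that patient's single baseline value, enters several times. The rows are correlated, and the estimate is weighted by visits instead of by patients.
- **Line them up by visit number.** Each patient then enters once per number, but a second visit may fall at very different times since surgery. Higher numbers exist only for patients who kept coming.

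The interim results could therefore carry the wrong error rate or describe a shifting set of patients. Section 1.0 says that the data are meant to support publications and marketing. With about 5000 patients, a weighting or selection bias does not shrink as the sample grows.

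**Working it through.** The plan gives no power, error-rate or variance calculation to reproduce, so this check shows what pooling would do under stated assumptions.

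**Inputs.** From section 5.1: threshold 0.05, taken here as two-sided because sidedness is not stated. Assumed: m visits per patient, from 2 to 5; within-patient correlation of changes from baseline rc, from 0.3 to 0.7. The value 0.5 is a natural centre. If baseline and all follow-up values have unit variance and a common correlation ρ, two changes that share a baseline have covariance ρ − ρ − ρ + 1 = 1 − ρ and variance 2(1 − ρ), so rc = 0.5 for any ρ.

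**1. Change scores pooled over visits.** Design effect DE = 1 + (m − 1)·rc. Actual type I error = 2·[1 − Φ(1.96/√DE)].

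| m | rc = 0.3 | rc = 0.5 | rc = 0.7 |
|---|---|---|---|
| 2 | 0.086 | 0.110 | 0.133 |
| 3 | 0.121 | 0.166 | 0.206 |
| 4 | 0.155 | 0.215 | 0.266 |
| 5 | 0.186 | 0.258 | 0.315 |

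For example, m = 4 and rc = 0.5 give DE = 1 + 3 × 0.5 = 2.5 and an error of 0.215. Simulation with 300 patients and 4000 runs at rc = 0.5 gave 0.162 (m = 3) and 0.204 (m = 4).

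**2. Unpaired test of n baseline values against n·m follow-up values.** With ρ the correlation between follow-up values and rb the correlation of baseline with follow-up, DE = [1 + (1 + (m − 1)ρ)/m − 2rb] / (1 + 1/m).

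- ρ = rb = 0.5: DE = 0.5 for every m, error 0.006.
- ρ = 0.7, rb = 0.2: error 0.046 (m = 2) to 0.066 (m = 5).

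The conservatism comes from ignoring the pairing with baseline: the simulation gave 0.006 even with one visit per patient. On the same simulated data with m = 4, the pooled change-score test rejected in 20.4% of runs and the unpaired test in 0.8%. The unstated test form therefore decides the direction of the error.

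**3. Weighting under pooling.** Assume that 80% of patients change by −30 with 2 visits each, and 20% change by −5 with more visits.

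- Mean over patients: 0.8 × (−30) + 0.2 × (−5) = −25.0.
- Mean over visits if the 20% attend 4 times: (1.6 × (−30) + 0.8 × (−5)) / 2.4 = −21.7. They supply 0.8/2.4 = 33% of rows.
- If they attend 6 times: (1.6 × (−30) + 1.2 × (−5)) / 2.8 = −19.3. They supply 1.2/2.8 = 43% of rows.
- With equal visit counts there is no shift.

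**4. Lining up by visit number.** No error-rate formula is needed. The patients with a fourth visit are by definition those who attended at least four times, and nothing ties that visit to a time since surgery.

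**5. With one value per patient and a paired test.** The error is 0.050 by formula and 0.041 to 0.054 in simulation. The test is exact for the simulated normal data, so that spread is simulation noise.

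No calculation was run for Fisher's exact test. It makes the same independence assumption.

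**The case against.** The strongest reply is that the plan never says visits are pooled. Table 1 is a collection schedule, not an analysis rule, and sections 2.2 and 5.1 use the plural for visits and time points. A separate test at each time point, with one value per patient, fits that wording equally well. This stands, and it is why the figures above are conditional. It does not close the gap, because the time points at which such tests would be run are not defined.

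A reader might infer three stronger things that the documents do not support.

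- **That patients doing badly attend more often and dominate the estimate.** This is plausible in routine care, but no section links visit frequency to outcome. Even where it holds, those patients need not supply most of the rows (33% to 43% in the example).
- **That standard errors are always too small.** An unpaired pooled test can be conservative.
- **That all results are affected.** Baseline-to-final comparisons use one final value per patient, and the primary endpoint in section 5.2 (length of follow-up and further surgery) does not depend on how interim visits are grouped.

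It is also fair to say that the number of usable VAS or ODI values may be lower than the number of visits, since they are taken only as available. With m = 2 the inflation is 8.6% to 13.3%, at the low end of the range. Finally, windows do not remove selection: if attendance depends on outcome, late windows are still filled by those who come. A mixed model helps only so far as observed data explain attendance.

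**Conclusion.** The point holds as a gap in the interim analysis that has consequences. The plan collects an unfixed number of visits per patient, defines no interim time points, and names only tests that assume independent observations. Pooling change scores would raise a nominal 5% error to between 8.6% and 31.5% under the assumed 2 to 5 visits and correlations of 0.3 to 0.7. An unpaired pooled test could fall to 0.6% or stay near 5%. Lining up by visit number avoids repeated rows but mixes times since surgery and narrows to continuing attenders. The visit counts and correlations are assumptions, because the documents give neither. The reach is one secondary objective and the section 5.1 tests that serve it. This should be corrected before analysis.

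**What to change.** In section 5.1:

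- Assign follow-up visits to fixed windows by days since surgery (for example 6 weeks and 3, 6, 12 and 24 months). Keep one value per patient per window, the one nearest the target day.
- For continuous outcomes, analyse the windows together in a mixed model for repeated measures, with patient as a random effect and baseline score as covariate. At minimum, use a paired test in each window.
- For categorical outcomes, use one value per patient per window.
- Report the number of patients contributing to each window, and state that late windows may still be selected by who attends.

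In section 4.4.4, add the follow-up visit date. Date of visit is listed only at baseline (4.4.1), and date of surgery is in 4.4.2, so days since surgery cannot be derived from the listed items.

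The cost is a few sentences in section 5.1, a standard model and one chart item per visit. The length-of-follow-up endpoint in section 5.2 already needs the timing of the last visit. The downside is that visits outside the windows, or duplicated within one, are not used in the main table.

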5.0 Statistical Analysis

5.1 General Information

All continuous outcome measurements at follow-up time points will be compared to baseline values using a t-test for superiority. Categorical outcome measurements will be compared using a Fisher's exact test for superiority. Statistical significance for these analyses will be demonstrated with a p-value less than 0.05.

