Retrospective Evaluation of the Clinical and Radiographic Performance of coflex® Interlaminar Technology Versus Decompression With or Without Fusion.

Study ID Number: CRDC2016

Version 5.0

02November2016

Study Phase: Post-Market

Paradigm Spine

[name]

[name]

Change History

Version	Version Date	Summary of Changes
1.0	14June2016	Original
2.0	28June2016	Data collection to include 1 or 2 level decompression with or without fusion.
3.0	11July2016	Protocol title to reflect evaluation of coflex versus efficacy.
4.0	19August2016	Study Start Date and End Date applicable for Baptist IRB
5.0	22Novmeber2016	Data collection to include 5000 patients from 50 sites. Primary and Secondary Endpoints.

Table of Contents

Retrospective Evaluation of the Clinical and Radiographic Performance of coflex® Interlaminar Technology Versus Decompression With or Without Fusion.....	1
Table of Contents.....	2
Investigator Signature Page.....	3
Protocol Summary	4
Retrospective Evaluation of the Clinical and Radiographic Performance of coflex® Interlaminar Technology Versus Decompression With or Without Fusion.....	4
Study Abbreviations	5
1.0 Introduction	6
2.0 Study Purpose.....	6
2.1 Primary Objective	6
2.2 Secondary Objectives	6
3.0 Eligibility Criteria.....	7
3.1 Inclusion criteria.....	7
3.2 Exclusion criteria	7
4.0 Study Design	7
4.1 Endpoints	7
4.2 Data Collection Summary	8
4.3 Informed Consent	9
4.4 Data Collection Procedures	9
4.4.1 Baseline Visit	9
4.4.2 Surgical Treatment Visit.....	10
4.4.3 Post-Operative Hospital Stay	11
4.4.4 Follow-Up Visits	11
5.0 Statistical Analysis.....	11
5.1 General Information	11
5.2 Primary Endpoint	12
5.3 Secondary Endpoints.....	12
6.0 Study Management	12
6.1 Ethics.....	12
6.2 Data Entry	12

Investigator Signature Page

My signature below attests that I have read the contents of this protocol and agree to conduct the study according to the protocol and that the study will not be initiated without the approval of the appropriate Institutional Review Board or Independent Ethics Committee.

Investigator:

Print Name:

Signature:

Date:

Protocol Summary

Study Title	Retrospective Evaluation of the Clinical and Radiographic Performance of coflex® Interlaminar Technology Versus Decompression With or Without Fusion.
Purpose	To evaluate clinical, radiologic and patient-reported outcomes who have been treated 1 or 2 levels with the coflex® Interlaminar Technology or decompression with or without fusion.

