4.1 Endpoints

Patient reported outcomes will be assessed as part of the primary objective.

Clinical and radiologic outcomes, demographics and risk factors will be assessed as part of the secondary objectives. These include, but are not limited to:

- Age
- Gender
- Ethnicity
- Height and Weight
- BMI
- Narcotics use
- Comorbidities
- Bone Density
- Presenting Symptoms
- Radiologic Data (Anterior/Posterior and Flexion/Extension films, as well as, MRI and/or CT Scan used to confirm diagnosis of spinal stenosis)
- Operative Data
- Intra-Operative Complications
- Return to Work
- Changes in Activities of Daily Living (ADL)
- Patient Satisfaction
- Repeat Surgery Details

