5.3 Secondary Endpoints

The clinical outcomes will be summarized; however, since the collection of these measures is not standard of care, this data will only be collected as available. In addition, data will be used to analyze the association between coflex® Interlaminar Technology use and outcomes with age, ethnicity, race, workers' compensation, smoking status, and gender. New and/or worsening complications will be summarized.

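### The title sets coflex against decompression with or without fusion, but the only contrast the analysis section explicitly defines is follow-up versus baseline, labelled superiority; no between-treatment contrast is specified

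*Combined protocol and SAP*

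**What the plan says.** The study is titled "Retrospective Evaluation of the Clinical and Radiographic Performance of coflex® Interlaminar Technology Versus Decompression With or Without Fusion". The Purpose in the Protocol Summary and sections 4.0 and 4.2 bring in patients who had decompression with or without fusion as well as coflex patients.

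The analysis section then says four things that bear on a comparison:

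- Section 5.1, continuous outcomes: "All continuous outcome measurements at follow-up time points will be compared to baseline values using a t-test for superiority".
- Section 5.1, categorical outcomes: "Categorical outcome measurements will be compared using a Fisher's exact test for superiority". It does not say what is compared with what.
- Section 5.2, primary endpoint: duration of follow-up care and "incidence of secondary surgical interventions will be analyzed to evaluate overall effectiveness of the use of the coflex® Interlaminar Technology". No comparator, test or model is given.
- Section 5.3: "data will be used to analyze the association between coflex® Interlaminar Technology use and outcomes", together with a list of patient factors. No reference group, model or adjustment is given.

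The objectives do not fill the gap. Section 2.1 concerns the coflex device alone. Section 2.2 asks for comparisons over time. Section 1.0 describes data on coflex patients only and states that the data are to support publications and marketing.

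**The concern.** A change from baseline after surgery has several sources: the decompression that every group receives, the natural course of symptoms, regression to the mean in patients operated on when their symptoms were bad, and any effect of the implant. A test against baseline cannot separate them. If VAS and ODI are analysed as 5.1 directs, the result says nothing on whether coflex does better or worse than decompression alone or decompression with fusion.

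Two things follow. First, a within-patient p-value labelled superiority, under a title that says versus, is easily read as a comparative finding, and the stated use is publications and marketing. Second, because the Fisher comparison, the 5.2 comparator and the 5.3 reference group are left open, the comparative contrast can be settled after the data have been seen. That includes whether decompression alone and decompression with fusion are one comparator or two, and whether the non-random choice of treatment is adjusted for.

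**Working it through.** **Step 1. Look for a between-treatment contrast in each analysis statement and objective.**

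| Place | What is compared | Groups named? | Adjustment named? |
|---|---|---|---|
| 2.1 | Nothing; coflex assessed | No comparator | No |
| 2.2 | Baseline, interim and final follow-up; impact of demographics and risk factors | No | No |
| 5.1, t-test | Follow-up against baseline | No | No |
| 5.1, Fisher | Not stated | No | No |
| 5.2 | Not stated | Coflex only | No |
| 5.3 | Association of coflex use and outcomes with patient factors | Coflex; no reference group | None stated |

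One contrast is fully defined, and it is within patient. It cannot apply to either 5.2 endpoint, since neither duration of follow-up nor secondary surgery has a baseline value.

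**Step 2. What does the defined test say about the versus question?** The plan has no power calculation to reproduce. It states about 5000 patients from 50 sites, with no effect size, SD or split by group. The following is therefore an illustration on assumed inputs:

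- paired t-test of change, two-sided 0.05 (5.1 gives the 0.05 but not the sidedness)
- d = mean change divided by the SD of change, equal in every group, so the true between-group difference is 0
- n = patients in a group with both scores

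Power = P(|T| > t(0.975, n−1)), where T is noncentral t with n−1 degrees of freedom and noncentrality d√n.

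- n=50, d=0.5: noncentrality 0.5 × √50 = 3.536, critical value 2.010, power 0.934.
- n=100, d=0.5: noncentrality 0.5 × √100 = 5.000, critical value 1.984, power 0.9986.

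| Shared gain d | n=50 | n=100 |
|---|---|---|
| 0.3 | 0.548 | 0.844 |
| 0.4 | 0.792 | 0.977 |
| 0.5 | 0.934 | 0.9986 |

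In the same situation, a between-group t-test on change is significant about 5% of the time, as it should be (0.049 by simulation at d=0.5, 50 versus 50).

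**Step 3. Can the defined test detect that coflex is worse?** Suppose coflex gains 0.5 SD and a comparator 0.8 SD. The coflex test against baseline uses only coflex data, so its probability of significance is unchanged: 0.934 at n=50 and 0.9986 at n=100. It is the same whether coflex is equal to the comparator or 0.8 − 0.5 = 0.3 SD behind.

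**Step 4. Does the large sample help?** No. By the normal approximation, a gain of only 0.2 SD at n=500 is significant against baseline with probability 0.994. More patients make that test more certain to succeed, whatever the treatment difference.

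**The case against.** The strongest reply is that the between-group analysis is implied. Fisher's exact test is ordinarily for independent groups, the sample includes non-coflex patients, and secondary surgery is categorical with no baseline value, so a between-group Fisher test is a natural reading. The association analysis in 5.3 can likewise be read as coflex yes or no. A reader might infer from the gap that the study cannot answer the versus question at all. The documents do not support that: comparator charts are to be collected, and these two sentences may be meant as between-group. What stands is that neither names the groups, the reference or an adjustment.

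A second reply is that 5.1 matches the over-time objectives in 2.2, that VAS and ODI are collected only as available, and that *versus* appears only in the title while the design text says *or*. This is fair, and it is why a coflex case series remains a possible reading. It does not explain the title or why comparator charts are collected.

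A reader might also infer a high rate of spurious contrasts, with one group significant against baseline and the other not. With equal gains of 0.1 to 0.2 SD and 400 versus 100 patients, this happens 49% to 63% of the time. That is not a finding about this plan. No section says that groups will be tested separately and the results contrasted, and the split is invented. At 4000 versus 1000, which matches the stated total, the rate is 11.5% at 0.1 SD and under 0.3% from 0.15 SD upward.

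**Conclusion.** The point holds as a failure to specify the between-treatment contrast. It should be corrected before analysis, because the only contrast that is defined cannot inform the question in the title. That conclusion rests on the text and on logic, and needs no number. The 93% and 99.9% figures only show how readily a significant baseline test arises with no treatment difference. They depend on an assumed 0.5 SD gain, 50 or 100 patients with both scores, and a two-sided test. They concern continuous outcomes such as VAS and ODI and do not measure any error in the 5.2 endpoints, for which the defect is simply the missing comparator and method.

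A reader might count the disagreement over what is primary as part of this defect: section 4.1 says "Patient reported outcomes will be assessed as part of the primary objective", while 2.2 lists them as secondary and 5.2 names follow-up duration and secondary surgery. That conflict is real but separate, and should be reconciled on its own.

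**What to change.** Decide first whether a comparison is intended.

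**If it is**, amend 5.1 to 5.3 and align 2.1 and 2.2:

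- State that the main inference is between groups: coflex versus decompression alone, and coflex versus decompression with fusion, reported separately.
- Compare follow-up VAS and ODI between groups, adjusted for the baseline score and for prognostic covariates already on the collection list. Age, BMI, tobacco use, comorbidities and treated levels are examples; the exact list is for the study team to justify in advance. Report how many patients per group have both scores.
- State that Fisher's test is between groups, and give the reference group and model for the 5.3 association.
- Compare secondary surgery between groups in a way that allows for unequal follow-up, for example time from index surgery censored at last visit. Section 4.4.2 already lists "Date of surgery" for index and repeat operations. Section 4.4.4 says "longitudinal data will be collected for all follow-up clinic visits through final follow-up" but does not list the visit date, so add it; the follow-up duration endpoint needs it in any case.
- Keep change from baseline as a paired description and drop the word superiority.

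**If only a coflex case series is intended**, change the title and design to say so and make no comparative claim.

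The cost is rewording, one added data item and some extra analysis, which incomplete charts across about 50 sites may make harder. The between-group result may be less favourable than a pre/post p-value. Residual confounding from non-random treatment choice will remain and must be acknowledged.
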